1.4 Study design

This will be a randomised, double-masked, crossover, bilateral non-dispensing study, controlled by cross-comparison. Forty subjects will wear each lens brand for approximately one hour, on three separate study days in random order. Lenses will only be worn during study visits.

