1.5 Statistical considerations

The principal hypothesis to be tested in this work is that high contrast visual acuity in the lenses will be substantially equivalent.

Visual acuity assessment, biomicroscopy, lens surface data and subjective responses will generate data that are likely to be continuous and normally distributed. As such, these will be compared using linear regression models or other parametric methods. Subjective preferences will be compared using chi-squared tests. Lens fit data are expected to be ordinal data and assessed with non-parametric approaches. Deviations from this statistical plan will be discussed in the final report. Deviations may be necessary due to differences between the actual data distribution compared with the anticipated data distribution.

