1.5.1 Power analysis

Assessment using a dataset from a similar, previous study found that a power of 0.89 or greater is provided by 35 completing subjects to detect a 0.05 difference in high contrast visual acuity. This analysis assumes a two-tailed paired analysis and an alpha of 0.05. To allow for discontinuations, 40 subjects will be recruited.

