3.2 Visit conduct

3.2.1 Pre-enrolment

The subject will receive a study-specific information form outlining the study at least 24 hours before the initial visit

At a suitable time, each subject will be asked to watch a short on-line information presentation detailing study visits and procedures. They will be asked to complete several multiple-choice questions to gauge their understanding of the study. Upon successful completion of these questions, the subject will be booked to attend the initial visit. Subjects should be asked not to wear their habitual contact lenses on the day of the study visit.

3.2.2 Visit 1

Subjects should attend this visit wearing their spectacles. They will then be required to sign an informed consent form prior to enrolment. A copy of the signed form will be issued to the subject. When the subject has signed the consent form, they are considered to be enrolled on the study.

Subjects will be instructed on the following:

1. Lens handling, application and removal, where necessary.

2. Specific study instructions, such as the importance of not using any other contact lens products.
3. General contact lens information such as the management of red eyes.

The following procedures will be performed (any ocular measurement procedures outlined below will be carried out on each eye):

1. Details of the ocular history and contact lens wearing history of the subject will be noted (including habitual lenses, modality, wear time and comfortable wear time).
2. Auto-keratometry measures will be recorded.
3. The investigator will perform refraction and distance monocular logMAR visual acuity (both high and low contrast), in accordance with the current Eurolens Research Standard Operating Procedure 'The set up, measurement of visual acuity and procedures for carrying out an over refraction using the Eurolens computerised logMAR VA chart'.
4. Slit lamp biomicroscopy will be carried out for the signs outlined in Table 4 and in accordance with the current Eurolens Research Standard Operating Procedure 'Examination of the anterior segment using slit lamp biomicroscopy'. Grades will be scored to the nearest 0.1 unit in the best judgement of the investigator using Efron Grading Scales.

Classification	Primary signs	Secondary signs

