Signs	Conjunctival redness Limbal redness Corneal neovascularisation Epithelial microcysts Corneal oedema Corneal staining Location of staining Conjunctival staining Conjunctival indentation Papillary conjunctivitis	Blepharitis Meibomian gland dysfunction Mucin balls
Scale	Efron Grading Scales (scored to nearest 0.1)	Efron Grading Scales (scored to nearest 0.1) (except mucin balls, where the number is recorded.

Table 3: Biomicroscopic signs.

The presence of any ocular adverse events will be recorded (see Appendix A).

5. The investigator will confirm that the subject satisfies all the inclusion and exclusion criteria. Subjects who fail to meet all the criteria at this time will usually be discontinued and replaced.
6. The first randomised lens pair (Appendix B) will be fitted and allowed to settle for five minutes. Subjects will insert the study lenses themselves.

7. Monocular logMAR visual acuity (high contrast) will be recorded before performing an over-refraction, and then monocular and binocular logMAR visual acuity (high contrast only) will be carried out with the over-refraction in place, and in accordance with the current Eurolens Research Standard Operating Procedure 'Assessment of visual performance using the Bailey-Lovie logMAR visual acuity test chart and procedures for carrying out an over-refraction'.
8. If an over-refraction of $\pm 0.50D$ or more is found, a second lens pair will be applied and Step 7 above will be repeated.
9. The subject will be asked to score the following with reference to appropriate visual analogue scales (0-100) (Appendix C):
 - Handling
 - Comfort
 - Burning/stinging
 - Distance vision

11. Lens fit will be assessed using the following evaluations: horizontal and vertical centration, corneal coverage and movement. Normally, for an acceptable fit, centration and movement will fall within currently accepted clinical criteria [between 1 and +1 on a -2 to +2 grading scale (Appendix C)]. If the lens is graded as 'unacceptable' (i.e. any of the grades are +2 or -2), the investigator should state why.

12. Lens tightness on push-up will be recorded using the grading scale in Appendix C.

14. The subject will be asked to return after the study lenses have been in situ for one hour.

3.2.3 Visit 2

After approximately one hour of lens wear, the subject will return to the clinic and the following assessments will be made:

1. Recording of any ocular symptoms, adverse events since lens application.

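### Section 1.5 does not say how acuity and slit-lamp data from two eyes, three lenses and three days will be modelled, or which of six on-lens acuity measures is the principal outcome, although the sample size assumes a paired analysis

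*Combined protocol and SAP*

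**What the plan says.** Section 1.5 makes equivalence of the lenses in high contrast acuity the principal hypothesis. For acuity, biomicroscopy, lens surface data and subjective responses the planned method is that "these will be compared using linear regression models or other parametric methods". Section 1.5.1 gives a power of at least 0.89 with 35 completers for a difference of 0.05, and adds: "This analysis assumes a two-tailed paired analysis and an alpha of 0.05". It does not name the acuity measure behind that figure.

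The data have a layered structure:

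- **Design.** Each subject wears all three lenses "on three separate study days in random order" (section 1.4).
- **Eyes.** Section 3.2.2 says that "any ocular measurement procedures outlined below will be carried out on each eye".
- **On-lens acuity.** After settling, monocular acuity is taken before over-refraction; then "monocular and binocular logMAR visual acuity (high contrast only) will be carried out with the over-refraction in place" (section 3.2.2, step 7). If the over-refraction reaches the stated limit, "a second lens pair will be applied and Step 7 above will be repeated" (step 8). The same three measures are taken again after about one hour (section 3.2.3) and on each later lens day (sections 3.2.4 to 3.2.7).
- **Slit lamp.** Grades are taken before fitting and once after lens removal on each lens day.
- **Pre-lens acuity.** It is taken at Visit 1 (section 3.2.2, step 3) and, under sections 3.2.4 and 3.2.6, at Visits 3 and 5.

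Sections 2.9 and 3.4, on data handling and missing data, add nothing about the model.

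**The concern.** Two choices are left to the analyst. The first is which acuity result tests the principal hypothesis. The second is what counts as an independent observation. Section 1.5 promises to discuss deviations from the plan, but picking any of the six measures, or any row structure, would not be a deviation, so that clause gives no protection.

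The row structure decides whether the standard errors are right. An analysis paired by lens that treats the two eyes as separate subjects gives standard errors that are too small. What that does to an equivalence claim depends on how equivalence is judged. Over-narrow errors make it easier to claim by confidence interval and harder to claim by non-significance.

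A smaller matter is that the plan measures each eye before fitting on every lens day but does not say whether those values enter the lens comparison. This affects precision, not validity.

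**Working it through.** **1. The plan's own figure.** Inputs from section 1.5.1: n = 35, difference 0.05, two-sided alpha 0.05, power 0.89. The SD of the paired differences is not given, so the power cannot be reproduced independently. Solving the noncentral t (34 df) for the SD that gives 0.89 yields 0.0902, so SE = 0.0902/√35 = 0.0152. As the plan says 0.89 or more, 0.0902 is an upper bound. The figure is plausible for one paired difference per subject.

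**2. Candidate outcomes and rows, 35 completers.**
- On-lens acuity: 2 times × 3 measures (monocular before over-refraction, monocular with it, binocular with it) = 6 candidates per lens. Step 8 can add a second set at fitting.
- Either monocular measure: 35 × 3 lenses × 2 eyes × 2 times = 420 rows.
- Binocular: 35 × 3 × 2 times = 210 rows.
- After-wear slit lamp: 35 × 3 × 2 eyes = 210 rows per sign.

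The power calculation counts 35.

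**3. Both eyes counted as independent, one time point.** There are 70 eye differences. If the fellow-eye correlation of the differences is ρ (assumed), the true variance of the mean difference is (1 + ρ) times the variance that the analysis uses. Type I error = 2 × [1 − Φ(1.96/√(1 + ρ))].

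| ρ (assumed) | 1.96/√(1 + ρ) | Type I error |
|---|---|---|
| 0.3 | 1.719 | 0.086 |
| 0.5 | 1.600 | 0.110 |
| 0.7 | 1.503 | 0.133 |

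A simulation gave 0.084, 0.109 and 0.134.

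**4. Both times also counted as independent.** The factor becomes (1 + ρ_eye)(1 + ρ_time). It runs from 1.3 × 1.5 = 1.95 (type I error 0.16) to 1.7 × 1.9 = 3.23 (0.28), for assumed correlations of 0.3 to 0.7 between eyes and 0.5 to 0.9 between times. Choosing binocular acuity therefore solves the problem only if one time is also fixed.

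**5. Value of the pre-lens measurements.** With complete data every subject has every lens, so the lens contrast is wholly within-subject. With one value per subject per lens there are 105 rows. Subtracting 35 for subjects, 2 for lens and 2 for period leaves 66 error df. Adjusting for the day's deviation from the subject's three-day mean changes the variance of a lens difference by a factor of about (1 − r²) × 65/64. Here r is the within-subject correlation between the pre-lens value and the outcome (assumed), and 65/64 is the cost of estimating one slope.

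| r (assumed) | Variance factor | Change |
|---|---|---|
| 0 | 1.016 | +2% |
| 0.3 | 0.924 | −8% |
| 0.5 | 0.762 | −24% |
| 0.7 | 0.518 | −48% |

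Simulation over a range of cross-lens and between-subject correlations agreed (1.012–1.019, 0.914–0.930, 0.746–0.771, 0.511–0.523).

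**6. A limit on step 5 for acuity.** Visit 1 takes pre-lens acuity with a fresh refraction under a procedure that covers "procedures for carrying out an over refraction using the Eurolens computerised logMAR VA chart". Visits 3 and 5 cite a Bailey-Lovie chart procedure and reuse the Visit 1 refraction. A period term absorbs a shift in the mean but not a different error variance. If the Visit 1 pre-lens within-subject variance were twice as large, the gains at r = 0.3, 0.5 and 0.7 would shrink to 5%, 17% and 35%. At four times they would be 3%, 11% and 23%. Type I error stayed at 0.049 to 0.053.

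**The case against.** The strongest reply is that linear regression can include a mixed model, that the design is a crossover, and that section 1.5.1 assumes pairing, so a within-subject analysis is plainly intended. Much of this stands. A reader might infer that the lenses will be compared as unpaired groups and the stated power lost. The documents do not support that; it is the least likely reading of sections 1.4 and 1.5.1. But an intention to pair by lens does not settle how two eyes and two times are handled, or which acuity measure is meant.

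Four narrower objections also stand:

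- **Slit lamp.** A reader might infer that slit-lamp data share the time-point gap. They do not. Grading is done off-lens, with one after-wear grade per eye per lens day. The time-point gap concerns acuity and those visual analogue scores that are taken at both visits (comfort, burning/stinging and distance vision).
- **Eligibility.** A reader might suppose that pre-lens acuity at least serves eligibility. The only acuity criterion, item 7 of section 2.1.3, is met with the study lenses on.
- **Assumptions.** Every correlation above is assumed. If all rows were treated as independent with no subject term, the type I error could fall either side of 0.05 (0.002 to 0.15 in the cases tried). A general claim of anti-conservative bias is not supported.
- **Covariate.** Table 1 does not list a pre-lens acuity test at Visits 3 and 5, so its availability rests on section 3.2. The variance factors hold for completers, while sections 2.1.1 and 3.4 allow partial data.

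**Conclusion.** The concern holds as a gap in specification. Section 1.5 fixes no subject, eye or period term and no principal acuity measure, while the sample size rests on one paired difference per subject. Counting the two eyes as independent would raise the type I error to about 0.09 to 0.13, given a fellow-eye correlation of differences of 0.3 to 0.7. Leaving the same-day pre-lens values out would forgo a variance reduction of about 8% to 48% at within-subject correlations of 0.3 to 0.7, and less for acuity if the Visit 1 measurement is noisier. The omission itself is certain; the sizes depend on those assumptions.

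A reader might go further and infer that the power of 0.89 is wrong. It is neither confirmed nor refuted, because its SD is not stated, and an SD of about 0.09 or less would support it.

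**What to change.** Amend section 1.5 to state:

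1. **Principal outcome.** Name one on-lens acuity measure (two-eye mean of monocular acuity, before or with over-refraction, or binocular acuity) at one time (after settling or about one hour), using the final lens pair. Match it to the measure behind the power figure, and name that measure in section 1.5.1.
2. **Model for acuity and graded slit-lamp signs.** Either use one value per subject per lens (two-eye mean or, for acuity, binocular) with fixed lens and period and random subject; or analyse at eye level, adding random subject-by-period and eye-within-subject terms. For signs that are mostly zero and for mucin-ball counts, use a non-parametric or count method that keeps the within-subject structure. Tabulate location of staining.
3. **Same-day pre-lens value.** Adjust for it, entered as the subject's three-day mean plus that day's deviation. For acuity use the high contrast value, averaged over the two eyes if the outcome is binocular. Report acuity with and without the covariate, because of the different procedure at Visit 1.
4. **Visual analogue scores.** Use the subject-level model at one named time point, without the covariate.

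Items 1 and 2 protect validity; item 3 is a gain in precision. The cost is wording only: section 3.2 already collects every variable, and no visit or subject is added. The covariate costs about 2% in variance if it proves uncorrelated with the outcome.

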Clinical investigation plan

C17-614 (EX-MKTG-85)

**A fitting evaluation of hydrogel and silicone hydrogel
spherical contact lenses**

**A clinical evaluation for
CooperVision Inc.**

Study Leader

Principal Investigator

May 2017

Contents

[figure not shown]
Document control	3
Study summary	
Section 1. Overview	5
1.1 Background	5
1.2 Personnel	5
1.3 Study objectives	5
1.4 Study design	5
1.5 Statistical considerations	5
1.6 Risk analysis	6
Section 2. Resources	7
2.1 Subject selection	7
2.2 Subject discontinuation	8
2.3 Safety parameters, adverse events and concurrent illnesses	8
2.4 Study termination	9
2.5 Protocol deviations	9
2.6 Study resources	9
2.7 Study control	10
2.8 Documentation	10
2.9 Data collection and analysis	10
2.10 Study completion	11
2.11 Confidentiality	11
2.12 Study monitoring	11
Section 3. Subject management	12
3.1 Visit scheduling	12
3.2 Visit conduct	12
3.3 Monitoring subject compliance	17
3.4 Missing, unused and spurious data	17
Section 4. Study co-ordination	18
4.1 Document processing	18
4.2 Disclosure	18
4.3 Personnel	18
Appendices	
A Adverse events	
B Randomisation table	
C Grading scales, questionnaires	

Document control

Study title: A fitting evaluation of hydrogel and silicone hydrogel contact lenses (C17-614) (EX-MKTG-85)

Sponsor company: CooperVision Inc.

Document type: Clinical investigation plan.

Study summary

This double-masked, randomised, bilateral crossover non-dispensing study will compare the clinical performance and subjective acceptance of the NewDay, Biomedics 1-day and Proclear 1-day daily disposable soft contact lenses.

Forty subjects will be enrolled on this study and will wear each lens type for approximately one hour on three separate study days in random sequence. The following will be assessed throughout the study: ocular physiology, lens fit, visual acuity, and subjective response.

A study summary is shown in Table 1.

Visit	Procedures
Information and consent presentation Visit 1	Short on-line presentation of study aims and procedures Informed consent taken Explanation of study procedures and subject instructions Medical, ocular and contact lens history Refraction Auto-keratometry Biomicroscopy Fitting of lens pair 1 Visual acuity Subjective scores Lens fit
Visit 2	Subjective scores Visual acuity Lens fit Biomicroscopy
Visit 3	Medical and ocular history Biomicroscopy Fitting of study lens pair 2 Visual acuity Subjective scores Lens fit

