2. The subject will be asked to score the following scores with reference to appropriate visual analogue scales (0-100) (Appendix C):
 - Comfort
 - Burning/stinging
 - Distance vision
2. Monocular logMAR visual acuity (high contrast) will be recorded before performing an over-refraction, and then monocular and binocular logMAR visual acuity (high contrast only) will be carried out with the over-refraction in place, and in accordance with the current Eurolens Research Standard Operating Procedure 'Assessment of visual performance using the Bailey-Lovie logMAR visual acuity test chart and procedures for carrying out an over-refraction'.

15. Lens fit will be assessed using the following evaluations: horizontal and vertical centration, corneal coverage and movement. Normally, for an acceptable fit, centration and movement will fall within currently accepted clinical criteria [between 1 and +1 on a -2 to +2 grading scale (Appendix C)]. If the lens is graded as 'unacceptable' (i.e. any of the grades are +2 or -2), the investigator should state the reasons why.

4. Lens tightness on push-up will be recorded using the grading scale in Appendix C.

6. The subject will remove the lenses and will be asked to score the following with reference to appropriate visual analogue scales (0-100) (Appendix C):

- Handling on removal

7. Slit lamp biomicroscopy will be performed as described in Section 3.2.2.

8. Subjects will be discharged and asked to attend the next study day without their habitual lenses in situ.

3.2.4 Visit 3

Subjects should attend this visit without their contact lenses in situ. The following will be carried out:

1. Recording of any ocular symptoms, adverse events and concomitant medications since the last visit.
2. Monocular logMAR visual acuity (high contrast) in each eye using the refraction result found in Section 3.2.2 in accordance with the current Eurolens Research Standard Operating Procedure 'Assessment of visual performance using the Bailey-Lovie logMAR visual acuity test chart and procedures for carrying out an over-refraction'.
3. Slit lamp biomicroscopy will be carried out for the signs outlined in Table 4 and in accordance with the current Eurolens Research Standard Operating Procedure 'Examination of the anterior segment using slit lamp biomicroscopy'. Grades will be scored to the nearest 0.1 unit in the best judgement of the investigator using Efron Grading Scales.

Classification	Primary signs	Secondary signs

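### Does leaving the summary of the two-sided lens fit grades open put the fit comparison at risk?

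*Combined protocol and SAP*

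**What the plan says.** Section 1.5 (Statistical considerations) deals with fit in one sentence: "Lens fit data are expected to be ordinal data and assessed with non-parametric approaches". It names no test, no summary of the grades and no rule for combining two eyes. The only test it names for categorical data, chi-squared, is for subjective preferences. The principal hypothesis concerns high contrast visual acuity, and the power statement in section 1.5.1 is for that measure only.

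The grades are described in section 3.2.2 (Visit 1), step 11: "Lens fit will be assessed using the following evaluations: horizontal and vertical centration, corneal coverage and movement". The acceptable range is given in the same step: "centration and movement will fall within currently accepted clinical criteria [between 1 and +1 on a -2 to +2 grading scale". As printed, the lower limit has no minus sign. The rest of the step shows that -1 is meant, because only the two end grades count as unacceptable: "If the lens is graded as 'unacceptable' (i.e. any of the grades are +2 or -2), the investigator should state why". Section 3.2.3 (Visit 2) repeats the rule for the one-hour assessment, and Visits 4 and 6 follow Visit 2.

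Section 3.2.2 also says that "any ocular measurement procedures outlined below will be carried out on each eye", so each item yields two grades per subject per lens. The grading scales themselves are in Appendix C, which is not in the text available for review.

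**The concern.** On this scale the acceptable fits lie in the middle and both ends are poor. A rank test on the grades as recorded orders lenses from -2 to +2, so a lens that misfits equally often in each direction looks like one that always fits well. Conversely, two lenses equally far from the middle but on opposite sides look different.

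Fit is not trivial here. The study is titled a fitting evaluation, and the study summary lists fit among four assessments: "The following will be assessed throughout the study: ocular physiology, lens fit, visual acuity, and subjective response". The protocol also defines an unacceptable fit without naming a comparison of it between lenses. If analysts ranked signed grades and stopped there, the report could say that fit did not differ when one lens had clearly more unacceptable fits.

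**Working it through.** **Inputs from the documents.** 35 completing subjects, paired comparison, two-sided alpha 0.05 (section 1.5.1, stated for visual acuity); scale -2 to +2 with either end unacceptable (sections 3.2.2 and 3.2.3). The plan states no figure for fit, so there is none to reproduce. The documents give no grade distributions, so all those below are assumptions.

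**1. The cancellation is real.** Take 35 subjects with grades -2/-1/0/+1/+2 in 5/7/11/7/5 on one lens and 0 throughout on the other. The 24 non-zero differences comprise 14 of size 1 (mean rank 7.5) and 10 of size 2 (mean rank 19.5).

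- Signed Wilcoxon: positive rank sum = 7 × 7.5 + 5 × 19.5 = 150; negative rank sum = 150; p = 1.00.
- Wilcoxon on absolute grade: all 24 differences point the same way; p = 0.00001.
- Exact McNemar on unacceptable fit: 10 of 35 (28.6%) against 0; p = 2 × (1/2)^10 = 0.002.

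**2. It depends on the direction split.** 35 independent pairs, 4,000 simulated trials (the 9:1 row was run separately). The comparator has 0/10/80/10/0%. The other lens has 20% at ±2, 40% at ±1 and 40% at 0, divided between negative and positive grades as shown.

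| Split | Signed Wilcoxon |
|---|---|
| 1:1 | 5% |
| 2:1 | 26% |
| 3:1 | 52% |
| 9:1 | 95% |
| One-sided | 100% |

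In the 1:1, 2:1, 3:1 and one-sided cases absolute grade gives 98-99% and exact McNemar 72-73%. The signed loss is severe near balance and small once misfit is mostly one-sided.

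**3. Much of the absolute-grade advantage comes from the assumed mid-range gap.** The case of 20% against 0% unacceptable also assumes 60% against 20% non-zero grades. Smaller gaps, with misfit evenly split, give:

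| Assumed grades (%), -2 to +2 | Absolute Wilcoxon | Exact McNemar |
|---|---|---|
| 5/20/50/20/5 v 0/10/80/10/0 (10% v 0% unacceptable; 50% v 20% non-zero) | 86% | 14% |
| 5/10/70/10/5 v 0/10/80/10/0 (10% v 0% unacceptable; ±1 rates equal) | 31-32% | 12-15% |
| 5/15/60/15/5 v 2.5/12.5/70/12.5/2.5 (10% v 5% unacceptable) | 16% | 3-4% |

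The McNemar figures can be checked by hand when the comparator has no unacceptable fits. Five discordant subjects give 2 × (1/2)^5 = 0.0625 and six give 2 × (1/2)^6 = 0.031, so six are needed. P(X ≥ 6) for X ~ Binomial(35, p) is 0.73 at p = 0.20 and 0.13 at p = 0.10.

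**4. Mirror-image lenses.** With 0/30/60/10/0 against 0/10/60/30/0, signed grades reject in 77% of trials and absolute grade in 5%. With 15/30/40/10/5 against 5/10/40/30/15 the figures are 87% and 5%. Calling these two lenses equal in quality assumes that -1 and +1 are equally good, which only Appendix C could confirm.

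**5. What the plan's sentence allows.** Unacceptable status is derived from the fit grades, so it is itself lens fit data. Wilcoxon or Friedman on absolute grade, McNemar and Cochran's Q are all non-parametric. Each fits section 1.5 as written.

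**The case for a change.** The strongest case for a change is that signed, absolute and acceptability analyses can lead to opposite conclusions from the same data, so the choice should be fixed before unmasking. Signed grades are what the case report form will hold, and an analyst in a hurry might rank them as they stand. The plan offers no reason to expect one-sided misfit, and even at a 3:1 split signed power is only about half. Stating the summary would cost a sentence and need no new data.

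The facts in this stand: the summary and the combination of eyes are unspecified, and ranking signed grades alone would be a poor choice when misfit is balanced. The step from there to a defect does not. The harm belongs to a method that the plan does not state. A mirror-image result is also not a false positive: lenses that sit on opposite sides of the middle do fit differently, and section 1.3 asks for a comparison of clinical performance, not a ranking of fit quality.

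Nor is there one evident replacement. Worst eye or a model for both eyes, acceptability or absolute grade, single items or a composite are all defensible. Absolute grade depends on a scale that cannot be seen here. The simulations use one grade per subject, so they do not give the power of a composite over several items and two eyes.

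**Conclusion.** No change is needed. Section 1.5 leaves the fit summary open; it does not prescribe a wrong one. An analyst who reads the protocol's own definition of unacceptable fit has suitable non-parametric methods already within the plan. Investigators must give a reason for each unacceptable lens, so those fits can be listed by lens whatever test is used.

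The possible loss is large only if signed grades are ranked alone and misfit is close to balanced: about 5% power at 1:1 against 95% at 9:1, under assumed rates of 20% against 0% unacceptable. With smaller assumed differences the alternative tests also miss most of the time (16% for absolute grade and 3-4% for McNemar at 10% against 5%). The documents do not suggest large differences in fit: Table 2 gives all three lenses the same 8.7 mm base curve and diameters of 14.2 or 14.3 mm. Fit is a secondary measure, and neither the acuity hypothesis nor the 35 completers in section 1.5.1 depends on it.

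This conclusion rests on the wording of section 1.5 and on the two-sided rule in sections 3.2.2 and 3.2.3. The power figures illustrate it and are not estimates for these lenses.
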